7.4 Generalisability

We will measure baseline serum selenium levels to explore the relationship between baseline selenium levels and response to supplementation, but we will not exclude participants based on their serum levels. By having an unselected group can we explore whether there is a subset that should be targeted or whether everyone benefits. If selenium supplementation proves to be an effective preventative measure for women with osteopenia, a requirement for baseline selenium measurement might impede widespread adoption, and potential implementation as a public health measure.

To ensure all participants are vitamin D replete, they will be given a single oral dose of 100,000IU colecalciferol at the screening visit (NIMP).

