11.6 Dosage schedules

Participants will receive one of three doses:

- Selenase 200mcg
- Selenase 50mcg
- Placebo

Orally, once daily, in the morning

The total duration of treatment will be 26 weeks.

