13. STATISTICS

13.1 Power calculation

A 20% (10nmol BCE/mmolCr) decrease in urine NTX is a plausible and clinically significant effect size.

In a previous study, 200mcg daily for six months increased serum selenium by 90mcg/L (19).

In our observational study of serum selenium and bone turnover markers, the regression coefficient of serum selenium and NTX/Cr was -0.101 (9), so if the relationship were causative we would expect an increase in serum selenium of 90mcg/L to be associated with a reduction in urine NTX/Cr of 9 nmol BCE/mmolCr (approximately 20%).

In support of this estimate, we would not expect as large a change in bone turnover as would be seen with a potent anti-resorptive drug such as a bisphosphonate (about 60%), but it might be

similar to a weaker anti-resorptive such as a SERM. In a study of six months' treatment with the SERM lasofoxifene (37), NTX decreased by 29%. We have also used this study as a model for the likely SD (12.5) and the correlation between NTX/Cr at baseline and six months (0.7).

A 20% decrease in NTX is clinically significant; a 20% decrease in NTX (about 1 standard deviation decrease) with bisphosphonate treatment is associated with a 30% decrease in incident vertebral fracture (38).

To achieve 90% power to detect this mean difference at the 2.5% (two-sided) level will require 21 patients per group. To allow for dropout, group imbalance and the secondary endpoint analyses we will recruit 33 patients per group with serum selenium below 120mcg/l (99 patients in total).

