We will not exclude women with baseline serum selenium above 120mcg/l, because it is important that the results of this study are generalisable into practice, but it is possible that there will be no benefit in women who are selenium replete at baseline. Therefore we will recruit enough participants to ensure that at least 99 women with baseline serum selenium below 120mcg/l are randomised for the primary endpoint analysis. We will determine the total number required from an interim analysis of the distribution of baseline serum selenium in the first 40 women recruited. In our previous cross-sectional study, 80% of European women had serum selenium below 120mcg/l, so we expect that we will need to recruit 120 in total. If at the interim analysis, less than 60% of women recruited have serum selenium below 120 mcg/l, the study recruitment strategy will be reviewed and discussed with the funder to determine if the trial should proceed. Therefore the maximum sample size will be 165 (if 60% of women have serum selenium below 120mcg/l)

We will conduct a secondary analysis of all participants to determine whether baseline serum selenium is a determinant of bone turnover response.

The power calculation was done by [name], statistician at the Sheffield School of Health and Related Research (ScHaRR).

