13.2 Analysis plan

A detailed statistical analysis plan (SAP) will be developed and finalised prior to the locking of the trial database in consultation with the trial steering committee.

We will conduct an intention-to-treat analysis (all randomised participants) and per-protocol analysis (completing participants with 75% compliance).

Primary endpoint:

Urine NTX at six months in postmenopausal osteopenic or osteoporotic women with baseline serum selenium below 120 mcg/l

Baseline data will be assessed for comparability between the treatment groups. NTX/Cr will be assessed visually for normality and if it is non-Normal a log-transform will be applied, with results reported as percentage difference between geometric means. Analysis of covariance (ANCOVA) will be used to compare mean NTX/Cr between the groups adjusting for baseline NTX/Cr measurements. The Hochberg procedure will be used to account for multiple comparisons; P-values are ordered from smallest to largest. If the largest P-Value is less than 0.05 then all null hypotheses can be

rejected. If not, if the second P-value is less than 0.05/2, then all bar the largest can be rejected, and so on (SA Julius, An Introduction to Statistics in Early Phase Trials).

Secondary endpoints:

Urine NTX at three months: analysis as described for the primary endpoint

Serum selenium, SePP, serum CTX, PINP, osteocalcin, thyroid function, glucose and insulin at three and six months: analysis as described for the primary endpoint.

BMD by DXA at six months: analysis as described for the primary endpoint.

We will examine impact of baseline selenium levels on the NTX response to selenium supplementation by fitting a linear model with NTX at follow-up as the dependent variable and baseline selenium, baseline NTX and dose as independent variables. With n=66 (receiving active treatment) the minimum correlation that can be detected with 90% power and 5% significance level is 0.44.

Short physical performance battery, grip strength, hydroperoxidases, glutathione peroxidase activity, highly sensitive CRP, IL-6 analysis as described for the primary endpoint.

There is no planned interim analysis of outcome measures. There will be an interim analysis of baseline serum selenium to determine the final sample size.

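### The model for baseline selenium and NTX response has no treatment-by-selenium term, so it cannot separate a changed response from the ordinary selenium–NTX association

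*Protocol*

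**What the plan says.** Section 13.2 states the aim: "We will examine impact of baseline selenium levels on the NTX response to selenium supplementation". The method is "fitting a linear model with NTX at follow-up as the dependent variable and baseline selenium, baseline NTX and dose as independent variables". The next sentence gives the sensitivity: "With n=66 (receiving active treatment) the minimum correlation that can be detected" with 90% power at the 5% level is put at 0.44.

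Section 13.1 announces the analysis for a different set: "We will conduct a secondary analysis of all participants to determine whether baseline serum selenium is a determinant of bone turnover response". The word dose does not settle which set is meant, because section 11.6 counts placebo as a dose: "Participants will receive one of three doses".

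Two other places show what the analysis is for. Section 13.1 says "it is possible that there will be no benefit in women who are selenium replete at baseline". Section 7.4 gives the reason for enrolling women whatever their selenium level: to explore "whether there is a subset that should be targeted or whether everyone benefits".

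**The concern.** Response to supplementation is a contrast between treated and untreated women. Whether it depends on baseline selenium is a question of effect modification, and needs a term that lets the treatment effect vary with selenium.

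The listed model has no such term. With all three arms it fits one common selenium slope, so it assumes the same treatment effect at every selenium level. With the active arms only, there is no placebo slope to subtract. In neither case can the coefficient distinguish selenium working less well in replete women from women with more selenium simply having lower NTX. The protocol relies on the second relationship being real: in section 13.1, "the regression coefficient of serum selenium and NTX/Cr was -0.101".

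At stake is the question used to justify recruiting replete women. The analysis could report a modifier that does not exist, or hide a modest real one.

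**Working it through.** **The protocol's own figure.** For a simple correlation with n = 66, 90% power and two-sided 5%, Fisher's z gives r = tanh((1.960 + 1.282)/√63) = tanh(0.408) = 0.387, not 0.44. A value of 0.44 corresponds to n of about 50. One-sided 5% gives 0.353. The 66 is evidently 2 × 33, where 33 per group is section 13.1's number below 120 mcg/L, so that set would contain no replete women. In any case a correlation within treated women is not a measure of effect modification.

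**Inputs.**
- Section 13.1: untreated slope b = -0.101 nmol BCE/mmolCr per mcg/L, NTX SD 12.5, baseline to six-month correlation r = 0.7, 33 per group below 120 mcg/L, 80% of women below 120 mcg/L, 120 recruited.
- Section 17: equal allocation.
- Assumed: the slope b persists at six months.
- Assumed: selenium mean/SD of 100/24, 95/30 or 90/36, each placing about 80% below 120. The protocol gives no SD.

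**What the coefficient estimates.** Let g be the change in an arm's treatment effect per mcg/L of baseline selenium (g = 0 for placebo), and r' the correlation between baseline and six-month NTX given selenium. Then

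expected coefficient = b(1 − r') + mean of g over the arms included.

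At selenium SD 30, r' = (0.7 × 12.5² − (0.101 × 30)²)/(12.5² − (0.101 × 30)²) = (109.4 − 9.2)/(156.3 − 9.2) = 0.68. With no modification the coefficient is -0.101 × 0.32 = -0.03. Adjusting for baseline NTX shrinks the prognostic part to about a third and does not remove it.

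**No modification: rejection at nominal 5% (simulation).**

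| Analysis set | SD 24 | SD 30 | SD 36 |
|---|---|---|---|
| Active arms, 66 women below 120 | 8% | 10% | 12% |
| Active arms, 80 unselected | 11% | 15% | 20% |
| All arms, 99 women below 120 | 10% | 12% | 16% |
| All arms, 120 unselected | 14% | 20% | 27% |
| Interaction test, all arms | about 5% | about 5% | about 5% |

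At SD 15 the planned model rejects in about 6 to 8%. If the association runs wholly through baseline NTX, the coefficient is about 0 and rejection about 5%.

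**Real modification (40 per arm, slope persisting).** A positive g means the benefit fades as baseline selenium rises.
- Fade of 0.03 in both active arms: active-only coefficient -0.03 + 0.03 = 0.00, rejected in 5%. The interaction test also detects little here (about 5 to 8%).
- Fade of 0.10 in the 200 mcg arm only: all-arms coefficient -0.03 + 0.10/3, about 0.00, rejected in 5 to 6%. The interaction model estimates 0.10 and rejects in 21 to 43%.
- Fade of 0.10 in both active arms: the active-only model rejects in 34 to 61%, the interaction test in 20 to 41%.
- Fade of 0.30 in both active arms: both models detect it in roughly 94% of trials or more, but the all-arms coefficient is -0.03 + 0.60/3 = 0.17, not 0.30.

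**Precision of the interaction.** With 40 per arm, the standard error for 200 mcg against placebo is 0.086/0.069/0.057 at SD 24/30/36. Multiplying by 1.96 + 1.28 = 3.24 gives 0.28/0.22/0.19 per mcg/L for 90% power. That is about 6.7 nmol per SD of selenium, against an expected treatment effect of 9 to 10 nmol.

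**The case against.** The strongest reply concerns direction. Loss of benefit in replete women would show as a positive selenium coefficient, while the prognostic leak is negative. With no modification, wrongly positive results occur in under 1% of trials at these SDs, below the nominal 2.5%. This stands. The false positives would suggest that women with more selenium respond better. But the same negative bias pulls a true fade towards zero, which favours the answer that everyone benefits. That is not a safe direction for the question in section 7.4.

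Second, the size rests on an assumed SD. Section 12 says nearly everyone in the UK lies below 130 to 150 mcg/L, which fits an SD nearer 12 to 15, and there the excess is small. This also stands: 27% is the upper end, needing the largest SD, all arms unselected and a fully persisting slope. The cancelling examples were likewise chosen to show the mechanism.

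Third, the interaction test is weak, and in one scenario the active-only model rejects more often. True, but that rejection cannot be attributed to modification.

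Finally, an SAP could add the term. It could, but section 13.2 does not leave the model open: it names the independent variables and gives a treated-only sample size.

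**Conclusion.** The model is wrong as written for its stated aim and should be changed. That conclusion needs no assumption about size: without an interaction and a placebo comparison, the coefficient is not effect modification in either analysis set. The numerical consequence does depend on assumptions. If the -0.101 slope persists, the bias is about -0.03 per mcg/L, with 8 to 27% false rejection at selenium SDs of 24 to 36 and about 6 to 8% at SD 15. If the association acts only through baseline NTX, there is no excess, but the all-arms coefficient still averages the modification over placebo. The damage is confined to this secondary analysis.

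**What to change.** In section 13.2, replace the model with six-month NTX/Cr regressed on baseline NTX/Cr, treatment (three levels), continuous baseline serum selenium, and treatment by baseline selenium. Fit it in all randomised participants, including placebo and women at or above 120 mcg/L, which agrees with section 13.1. Base inference on the interaction, report each treatment effect with its confidence interval across the observed selenium range, and label the analysis exploratory. Replace the n = 66 correlation sentence with the sensitivity of the interaction test.

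This costs one or two sentences, with no extra participants, visits or assays. The price is candour about power: only a strong dependence on baseline selenium, about 0.19 to 0.28 per mcg/L under the SDs assumed here, would be found with 90% power, so a null result must not be read as showing that everyone benefits equally.

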14. STUDY SETTING

This is a single centre study.

It will be conducted in the Sheffield NIHR Clinical Research Facility at the Northern General Hospital, Sheffield. The CRF is a purpose-built facility, and contains all the resources needed for this study, including research specialist nurses, DXA and sample handling. The CRF has a high standard of governance and oversight. All studies are conducted as per organisational SOPs which are compliant with GCP and other regulatory requirements. Studies taking place in the CRF are subject to regular monitoring and audit.

Participants will be identified through Sheffield Metabolic Bone Centre, but also through primary care Patient Identification Centres.

15. ETHICAL CONSIDERATIONS

The study will require REC, MHRA, HRA and local R+D approval and no study procedures will be undertaken until all approvals are in place.

The study will be conducted according to GCP and ICH regulations, and the Medicines for Human Use (Clinical Trials) Regulations 2004.

Written informed consent will be obtained from all participants, supported by a detailed Participant Information Sheet. Data and samples will be managed in accordance with the Data Protection Act and Human Tissue Act requirements.

There is no standard care pathway for women with osteopenia or osteoporosis whose fracture risk is not yet high enough to qualify for treatment. Usual practice would be to advise on modifiable risk

factors (such as dietary calcium intake and smoking) and consider repeat bone densitometry in a few years. Therefore this intervention will be in addition to usual care, and there is no ethical concern about using a placebo control.

Selenium has already been used at these doses and duration of treatment in clinical studies and in usual care of Graves' ophthalmopathy without adverse events.

The study intervention and procedures carry negligible risk to participants. The radiation dose for two DXA measurements of the spine and hip is 45.2microSv, equivalent to 7 days' natural background radiation.

Participants will be given travel reimbursement of £20 per visit, or provided with taxi transport for study visits. They will not receive any other payment for taking part in the study.

At the end of their study participation, the PI or delegated medical practitioner will write to the participants GP to inform them that their patient has completed the study, and give advice on any further recommended treatment and follow-up.

16. RECRUITMENT

A log will be kept of:

- Number of patient records assessed for pre-eligibility in Metabolic Bone Centre
- Number of patients approached from Metabolic Bone Centre and GP mailing
- Number of responders from these approaches
- Number of volunteers responding to adverts

- For responders not eligible on pre-eligibility check we will record reason for ineligibility

All volunteers who pass pre-eligibility checks and attend for consent and screening will be registered and allocated a study screening number. The screening number will be in the format COS001, COS002 etc.

16.1 Participant identification

Participants will be identified from four sources:

- AUBM volunteer database

AUBM keeps a database of previous study participants, screen failures from previous studies and volunteers who have asked to be added to the database for future research opportunities. All participants have given consent to be approached about future studies.

Potential participants will be sent an invitation letter and PIS, with a reply slip to request or decline further contact from the study team. Potential participants who do not return the reply slip will be contacted once by telephone to follow-up the invitation.

On receipt of a positive reply, the study team will make contact with the volunteer to discuss the study, answer questions and confirm pre-eligibility according to the inclusion/exclusion criteria.

Volunteers who are willing to participate and meet pre-eligibility criteria will be invited to a study visit for informed consent and screening.

- Metabolic Bone Centre, Northern General Hospital

Fracture risk assessment reports will be screened for potentially eligible participants. This will include identifiable personal information, but will be done by the PI (who is a member of the clinical care team) or other member of the clinical care team.

Potential participants will be sent an invitation letter and PIS, with a reply slip to request or decline further contact from the study team. Patients who do not return the reply slip will be contacted once by telephone to follow-up the invitation.

On receipt of a positive reply, the study team will make contact with the patient to discuss the study, answer questions and confirm pre-eligibility according to the inclusion/exclusion criteria.

Patients who are willing to participate and meet pre-eligibility criteria will be invited to a study visit for informed consent and screening.

- Mailing from GP surgeries

GPs will be asked to send an invitation letter with reply slip to women age over 55 registered with their practice, and to screen the mailing list to remove anyone that it would be inappropriate to approach (eg dementia or current serious illness).

This will include identifiable personal information, but will be done by the clinical care team at the GP practice. The practice will be given a search strategy for this screening activity to ensure that screening is transparent and terms are defined.

On receipt of a positive reply, the study team will make contact with the patient to discuss the study, send a PIS and confirm pre-eligibility according to the inclusion/exclusion criteria. Patients who are willing to participate and meet pre-eligibility criteria will be invited to a study visit for informed consent and screening.

- Posters/email/website/word of mouth

Emails will be sent to hospital and university staff, through central IT services. The University has an established 'volunteers' mailing list. Posters will be displayed around the hospital and university, at patient and public events relevant to health and osteoporosis, and other public places such as GP surgeries and local businesses. Information on the study will be displayed on the hospital and university website.

The wording of all of these media will be submitted for REC and HRA approval.

On receipt of enquiries from these sources, the study team will make contact with the volunteer to discuss the study, send a PIS and confirm pre-eligibility according to the inclusion/exclusion criteria. Volunteers who are willing to participate and meet pre-eligibility criteria will be invited to a study visit for informed consent and screening.

Volunteers through any route will not be actively asked to pass on study information to friends or family, but if friends or family express interest in the study they will be advised to contact the study team who will follow the same procedure as for poster and email responders.

16.2 Screening requirements

Medical history for inclusion/exclusion criteria

BMD spine and hip by DXA (results within the last 6 months can be used)

Blood tests –for diabetes mellitus, thyroid dysfunction, bone profile

Volunteers will be shown the study capsules and offered the opportunity to try taking a placebo capsule if they are concerned about their ability to swallow the capsules.

Eligibility will be confirmed by the PI or delegated medical practitioner.

16.3 Consent

The PI retains overall responsibility for the informed consent of participants at their site and will ensure that any person delegated responsibility to participate in the informed consent process is duly authorised, trained and competent to participate according to the ethically approved protocol, principles of Good Clinical Practice (GCP) and Declaration of Helsinki.

Consent will be obtained by a doctor or specialist research nurse with appropriate training and experience assessed and delegated by the PI

This study will not include vulnerable participants or participants who lack capacity.

Informed consent will be obtained prior to the participant undergoing any trial procedures.

Each prospective participant will receive a participant information sheet giving details of the study and will have at least 24 hours to consider their participation in the study. All participants will also be given a verbal explanation of the information in the PIS and the opportunity to ask questions before the first visit, during the consent process and throughout the duration of the study. The consent process will follow the Sheffield CRF SOP for informed consent.

Where a participant is able to consent but later becomes incapacitated, they will be withdrawn from the study. Data obtained up to that point will be retained and used in analysis. This is specified in the PIS.

17. RANDOMISATION

Participants will be block randomised equally to the three treatment arms.

The randomisation list will be generated by Sharp Clinical Services. The list will be supplied to STH pharmacy and a copy retained by Sharp.

At randomisation, participants will be allocated a study ID number which corresponds to their randomised medication number (the ID number will be in the format SE???, where ??? is the randomised medication pack number).

The code list will be stored in STH pharmacy, in a sealed signed envelope under the supervision of the study pharmacist, or out-of-hours duty pharmacist. This envelope is signed when opened and resealed for audit purposes. If emergency access is required out of hours, the PI or if unavailable, another metabolic bone consultant can be contacted through STH switchboard. If they agree that the code need to be broken, the duty pharmacist will access the list.

